16.1.5 Baseline Disease Activity Sensitivity Analysis of Primary Efficacy Variable

A total of four (4) participants randomized have baseline disease activity MMS = 4 according to IWRS. These four participants will be included in a sensitivity analysis of the Primary Efficacy

Variable. No imputation will be performed for this sensitivity analyses, non-responders will be handled as defined at the beginning of Section 16, FAS will be used, and this analysis will use the same CMH statistical methodology with randomized stratification factors as other responder analyses. VTX002 60 mg vs Placebo will be the only treatment comparison considered.

16.1.6 Supplementary Analysis of Primary Efficacy Variable

The primary model as described in [Section 16.1.3](#) will be repeated using the mFAS and Per Protocol sets as separate analyses.

16.1.7 Stratification Factor Sensitivity Analysis of Primary Efficacy Variable

FAS will also be used in re-analyses of the primary model but using stratification as-collected in EDC instead of as-randomized in IWRS. No imputation beyond non-responder imputation as described at the top of [Section 16](#) will be done.

16.2 Key Secondary Analyses

Key secondary efficacy endpoints are defined in [Section 7.2](#):

- Hypothesis testing of these endpoints for VTX002 60 mg versus placebo are considered key secondary analyses
- Hypothesis testing of the primary efficacy endpoint for VTX002 30 mg versus placebo, in addition to hypothesis testing of the key secondary efficacy endpoints for VTX002 30 mg versus placebo, are also considered key secondary analyses

The primary analyses of these hypothesis tests are subject to the family-wise Type 1 error rate handling and gatekeeping (i.e., multiplicity adjustments) described in [Section 10.3](#). After attribution of known outcome at Induction Week 13 (see introduction to [Section 16](#)), the primary planned Key Secondary Analyses as described [Table 6](#) will be conducted.

The CMH methodology used for the primary analysis of the primary endpoint will be used for all Key Secondary Analyses. The additional primary endpoint analysis methods described in [Sections 16.1.4](#) and [16.1.6](#) – missing data methods (MAR multiple imputation, copy reference multiple imputation, tipping point), randomization stratification factor (EDC) sensitivity analysis, and supplementary analyses (application of mFAS and PP analysis sets to primary analysis methods) – will also be applied to the Key Secondary endpoints. See [Table 6](#).

For tipping point analyses, identification of participants not contributing observed data at Visit 7 Week 13 will rely on the types of data needed for a given Key Secondary endpoint. For example, endoscopic improvement-histologic remission (the fourth Key Secondary endpoint) requires Geboes and ES to both be available. If they are not available for a given participant, that participant will be subject to tipping point analysis. The set of participants subject to tipping point analysis may differ from one endpoint to another.

16.2.1 Key Secondary Efficacy Endpoints and Derivations

16.2.1.1 Endoscopic Improvement at Week 13

The null hypothesis is that the proportion of participants achieving endoscopic improvement at Induction Week 13 is the same between VTX002 and placebo. The alternative hypothesis is that the proportion of participants achieving endoscopic improvement at Induction Week 13 is different between VTX002 and placebo. Subject to successful rejection of the primary efficacy endpoint for VTX002 60 mg vs placebo, this key secondary endpoint is evaluated according to the sequential Hypothesis Family approach illustrated in [Section 10.3](#), Figure 3.

16.2.1.2 Symptomatic Remission at Week 13

The null hypothesis is that the proportion of participants achieving symptomatic remission at Induction Week 13 is the same between VTX002 and placebo. The alternative hypothesis is that the proportion of participants achieving symptomatic remission at Induction Week 13 is different between VTX002 and placebo. Subject to successful rejection of the primary efficacy endpoint for VTX002 60 mg vs placebo, this key secondary endpoint is evaluated according to the sequential Hypothesis Family approach illustrated in [Section 10.3](#) Figure 3.

16.2.1.3 Histologic Remission at Week 13

The null hypothesis is that the proportion of participants achieving histologic remission at Induction Week 13 is the same between VTX002 and placebo. The alternative hypothesis is that the proportion of participants achieving histologic remission at Induction Week 13 is different between VTX002 and placebo. Subject to successful rejection of the primary efficacy endpoint for VTX002 60 mg vs placebo, this key secondary endpoint is evaluated according to the sequential Hypothesis Family approach illustrated in [Section 10.3](#) Figure 3.

16.2.1.4 Endoscopic Improvement-Histologic Remission at Week 13

The null hypothesis is that the proportion of participants achieving endoscopic improvement-histologic remission at Induction Week 13 is the same between VTX002 and placebo. The alternative hypothesis is that the proportion of participants achieving endoscopic improvement-histologic remission at Induction Week 13 is different between VTX002 and placebo. Subject to successful rejection of the primary efficacy endpoint for VTX002 60 mg vs placebo, this key secondary endpoint is evaluated according to the sequential Hypothesis Family approach illustrated in [Section 10.3](#), Figure 3.

Table 6. Planned Primary and Key Secondary Analyses

X = VTX002 60 mg vs Placebo

Y = VTX002 30 mg vs Placebo

Endpoint	Primary Analysis with Stratified CMH (FAS)	Key Secondary Analyses with Stratified CMH ^b (FAS)	Section 16.1.4 Missing Data Sensitivity Analyses (FAS: MAR MI, CR MI, Tipping Point)	Section 16.1.5 Sensitivity Analysis (FAS)	Section 16.1.6 Supplementary Analyses (mFAS, PP Sets)	Section 16.1.7 Sensitivity Analyses (FAS)
Primary endpoint – Clinical Remission	X ^a Family 1	Y Family 4	X, Y	X	X, Y	X, Y
Key Secondary Endpoints						
Endoscopic Improvement		X: Family 2 Y: Family 5	X, Y		X, Y	X, Y
Symptomatic Remission		X: Family 2 Y: Family 5	X, Y		X, Y	X, Y
Histologic Remission		X: Family 3 Y: Family 6	X, Y		X, Y	X, Y
Endoscopic improvement – Histologic Remission		X: Family 3 Y: Family 6	X, Y		X, Y	X, Y

^a Serves as primary analysis gatekeeper for testing all Key Secondary Analyses with Stratified CMH

^b The collection of Key Secondary Analyses with Stratified CMH subject to a truncated Hochberg multiplicity adjustment to control the family-wise Type 1 error rate at $\alpha=0.05$. [Figure 3, Section 10.3](#) presents a flow chart demonstrating how this is to be done.

CMH = Cochran-Mantel-Haenszel; CR = copy reference; FAS = Full Analysis Set; mFAS = modified Full Analysis Set; PP = Per Protocol set; MI = multiple imputation; MAR = missing at random

16.3 Other Secondary Efficacy

Plasma concentrations of VTX002 will be handled in a separate PK Analysis Plan. Other secondary endpoints addressed in this SAP include the following (see [Section 7.2](#)):

- The proportion of participants with clinical response using MMS at Week 13
- The proportion of participants with endoscopic remission at Week 13
- The proportion of participants with endoscopic and histologic remission at Week 13
- The proportion of participants with endoscopic and clinical remission at Week 13
- The proportion of participants with endoscopic, histologic, and clinical remission at Week 13
- The proportion of participants with symptomatic remission at Weeks 4, 8, 10
- The proportion of participants with symptomatic response at Weeks 4, 8, 10, 13
- The proportion of participants with clinical remission using total MCS at Week 13
- The proportion of participants with clinical response using total MCS at Week 13
- The proportion of participants with histologic improvement at Week 13
- The proportion of participants with HEMI at Week 13
- The proportion of participants with any decrease from baseline in Geboes Index score at Week 13
- The proportion of participants with UC-related hospitalizations
- The proportion of participants requiring UC-related surgeries, including colectomy

These endpoints will be analyzed similarly to the primary endpoint, per timepoint, using the CMH test with the same as-randomized stratification factors. The FAS set will be used for this purpose and treatment group comparisons (VTX002 60 mg vs placebo; VTX002 30 mg vs placebo) will be as-randomized. No adjustment for multiplicity will be made.

Additionally, for clinical remission, endoscopic improvement, endoscopic remission, histologic improvement (Geboes), and histologic remission (Geboes) at Week 13, separate logistic regression models with stepwise selection will be built to assess the impact of the following covariates measured at baseline:

- ALC derived from blinded hematology laboratory results
- c-RP

Randomization stratification factors (from IWRS) will also be included in the stepwise selection. The alpha level for both entering and removing a covariate will be 0.10. Point estimates and the corresponding 95% CIs for the odds ratios will be calculated.

Repeated measures Induction/LTE data on the same endpoints (clinical remission, endoscopic improvement, endoscopic remission, histologic improvement (Geboes), and histologic remission (Geboes) at Weeks 4, 8, 10, 13, 18, 26, 36, and 52 will be analyzed. This will be done using repeated measurements logistic regression specifying the distribution as binomial, the link function as logit and randomization stratification factors added as covariates in addition to randomized treatment. Two summaries will be provided: summary for the Induction Treatment Period will include only data from Weeks 4, 8, 10 and 13, whereas a comprehensive summary for both Induction and LTE will include data through Week 52. Sample SAS code is presented below:

[REDACTED]

[REDACTED]

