9.4.1.3 Exploratory Analyses

Categorical exploratory endpoints will be analyzed similarly to the primary endpoint.

Continuous exploratory endpoints will be analyzed using a general linear model (analysis of covariance [ANCOVA]) with fixed effects for treatment, biologic/JAK inhibitor prior use status (Yes or No), baseline corticosteroid use (Yes or No), and baseline disease activity (MMS 4-6 or 7-9).

Repeated measures Induction/LTE data on clinical remission, endoscopic response, endoscopic remission, histologic improvement (Geboes), and histologic remission (Geboes) at Weeks 4, 8, 10, 13, 18, 26, 36, and 52 will be analyzed. This will be done using repeated measurements logistic regression specifying the distribution as binomial, the link function as logit and randomization stratification factors added as covariates in addition to randomized treatment.

Change from baseline in FCP and CRP at Weeks 1, 4, 8, 13, 26, 36, and 52; and also for change from baseline in PMS at Weeks 4, 8, 13, 18, 26, 36, and 52 will be analyzed using an appropriate continuous repeated measurements methodology. Details will be provided in the SAP, and will include a specification of how the results will be reported.

For clinical remission, endoscopic response, endoscopic remission, histologic improvement (Geboes), and histologic remission (Geboes) at Week 13, separate logistic regression models with stepwise selection will be built to assess the impact of the following covariates measured at baseline:

- ALC derived from blinded hematology laboratory results
- FCP
- CRP

The alpha level for both entering and removing a covariate will be 0.10. Point estimates and the corresponding 95% confidence intervals for the odds ratios will be calculated.

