9.7 Statistical Tests

The default statistical significance level will be 0.05 for two-sided hypothesis tests; one-sided hypothesis tests will not be performed unless explicitly stated otherwise. The default for confidence intervals (CIs) will be to generate two-sided 95% CIs.

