28. APPENDIX VII. DETERMINATION OF SAMPLE SIZE

Based on literature data review, the expected proportion of clinical remission at Induction Week 13 is 28% for VTX002 60 mg and 8% for placebo (Sandborn 2016; Sandborn 2020). Under these assumptions, and with a 1:1 randomization ratio, 2-group chi-squared test, and two-sided significance level of 5%, a sample of 57 participants per treatment group will be sufficient to achieve at least 80% power. Adding a 10% inflation for dropouts results in 63 participants per treatment group and 189 participants in total.

Software

SAS (version 9.4; SAS Institute Inc.; Cary, NC, USA).

Input & Output

Fixed Scenario Elements	
Distribution	Asymptotic normal
Method	Normal approximation
Number of Sides	2
Alpha	0.05
Group 1 Proportion	0.08
Group 2 Proportion	0.28
Nominal Power	0.8
Null Proportion Difference	0

Computed N per Group	
Actual Power	N per Group
0.802	57

29. APPENDIX VIII. RELATIONSHIP OF INTERCURRENT EVENTS TO NON-RESPONDER IMPUTATION, MULTIPLE IMPUTATION, COPY REFERENCE IMPUTATION, AND TIPPING POINT

Table 12. Relationships Between Various Types of Imputation and Data Missingness

Type of Occurrence	Visits Affected	Effect of Protocol Deviations	Primary Analysis of Primary, Key Secondary, and Other Secondary Endpoints	Multiple Imputation	Copy Reference	Tipping Point
Intercurrent Event	All visits on/after intercurrent event, regardless of data missingness for other reasons . Intercurrent event handling takes priority over missing data handling.	An intercurrent event is a major protocol deviation. As long as other deviations don't prevent the participant from being Per Protocol, they will be included in the PP Set.	Non-responder imputation	Non-responder imputation	Non-responder imputation	Non-responder imputation
Missing Data	Visits w/ efficacy endpoints having missing values in one or more endpoint components.	As long as there are no intercurrent events, missing data is handled per this row in the table.	Non-responder imputation	Multiple imputation	Copy reference imputation	Tipping point imputation

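### Stepwise selection at 0.10 followed by ordinary 95% CIs: the interval for a retained baseline factor with no true effect has about 50% coverage, and weak true effects are overstated when retained

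*SAP*

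**What the plan says.** SAP 16.3 states that "separate logistic regression models with stepwise selection will be built to assess the impact of the following covariates measured at baseline". The endpoints are clinical remission, endoscopic improvement and remission, and histologic improvement and remission by Geboes score, all at Week 13. The listed covariates are ALC and CRP. The SAP then adds: "Randomization stratification factors (from IWRS) will also be included in the stepwise selection". With three such factors (prior biologic/JAK inhibitor use, corticosteroid use, baseline disease activity) there are five candidates.

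The threshold and the output follow together: "The alpha level for both entering and removing a covariate will be 0.10. Point estimates and the corresponding 95% CIs for the odds ratios" are to be calculated. SAP 9.7 fixes the kind of interval: "The default for confidence intervals (CIs) will be to generate two-sided 95% CIs". The paragraph mentions no correction for selection, no report of the full model and no label marking the intervals as conditional on selection.

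Randomized treatment is not named for these models. The next paragraph of SAP 16.3, on repeated-measures logistic regression, does name it: "randomization stratification factors added as covariates in addition to randomized treatment".

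Protocol 9.4.1.3 has the same rule, "The alpha level for both entering and removing a covariate will be 0.10", and does not name treatment either. Its candidate list differs: ALC, FCP and CRP, with no mention of the stratification factors.

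**The concern.** A 95% CI has its stated coverage when the decision to report it does not depend on the data it summarizes. Here a factor is retained only if its own test reaches p < 0.10, and the usual reading of stepwise selection is that odds ratios are given for the final model. For a factor with no effect, retention removes the samples in which the estimate lay near the null, and those are the samples in which the interval would have covered. For a factor with a weak effect, retention favours samples that overestimate it.

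A reader of the study report would see an odds ratio with an ordinary 95% CI and nothing to say that it survived a filter. The gap on treatment is a different matter. From this paragraph a programmer cannot tell whether treatment is forced in, a candidate or absent, or whether the arms are pooled. The design expects treatment to be a strong predictor: "the expected proportion of clinical remission at Induction Week 13 is 28% for VTX002 60 mg and 8% for placebo".

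**Working it through.** **The plan's own figure.** The plan states no coverage for these models. The nearest computed figure is the sample size in SAP Appendix VII, which supplies two of the response rates used below. With rates 0.08 and 0.28 (mean 0.18), two-sided 5% and 80% power:

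n = [1.960 × √(2 × 0.18 × 0.82) + 0.842 × √(0.08 × 0.92 + 0.28 × 0.72)]² / 0.20² = 56.7, so 57 per group, with power 0.802. This agrees with the SAP.

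**Coverage for a retained null factor.** Inputs: 0.10 to enter and to stay (SAP 16.3), taken as two-sided; two-sided 95% CI (SAP 9.7). Under no effect, retention needs |Z| > 1.645 and the CI covers when |Z| < 1.960.

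P(covers, given retained) = (0.10 - 0.05)/0.10 = 50%.

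**Check by simulation.** Stepwise logistic regression with score-test entry and Wald removal at 0.10, five candidates and 5,000 runs per setting (4,790 to 5,000 usable). Assumed, because the documents do not give them: 18% remission on 30 mg, two standard normal covariates, and binary factors with prevalence 35%, 35% and 60%.

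| Setting | Coverage of a retained null factor |
|---|---|
| N = 189, treatment not in model | 50.4% |
| N = 189, treatment forced in | 49.6% |
| N = 126 (60 mg and placebo), treatment not in model | 51.2% |
| N = 126, treatment forced in | 50.0% |
| One true predictor | 48.5% |
| Three true predictors, treatment forced in | 51.1% |
| Two candidates correlated at 0.5 | 51.5% |
| Higher response rates (20%, 35%, 45%) | 48.8% |

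The first two rows differ by less than one point, so leaving treatment out does not produce the 50%. Each null factor is retained in about 10% of models. With five null candidates, at least one is retained in 39% to 40% of simulated models (analytically 1 - 0.9⁵ = 41%).

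**Size of retained true effects.** N = 189, with 20% remission on 30 mg assumed; the effect sizes are also assumed.

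| True odds ratio | Mean when retained | Coverage when retained |
|---|---|---|
| 1.30 per SD | 1.57 | 94.6% |
| 1.6 | 1.72 | 97.7% |
| 2.0 | 2.01 | 97.4% |

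The 1.30 effect is retained in only 38% of models. The full model averages 1.33 for it.

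**Overall rate of false predictors.** Any null factor with p < 0.05 also passes 0.10, so selection leaves the overall rate at about 5%. In simulation, the CI of a null factor excluded 1 in 4.5% to 5.4% of stepwise analyses and 4.7% to 5.5% of full-model analyses.

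**Can the full model be fitted?** Terms: two for treatment, three stratification factors, ALC and CRP, seven in all. Expected remissions at 63 per arm, with 20% assumed for 30 mg: 63 × (0.08 + 0.20 + 0.28) = 35.3, and 35.3/7 is about 5 per term. Simulated coverage of the full model was 95.0% under the null and 94.7% under the alternative.

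**The case against.** The strongest reply is that little rides on this. The protocol places these models under exploratory analyses. SAP 10.4 leaves everything outside the primary and key secondary families uncontrolled at a nominal 0.05. CRP and the stratification factors are also prespecified subgroups in SAP 10.5, shown in forest plots with no selection. All of this stands and limits the severity. It does not rescue the interval: a reader can allow for multiplicity, but nothing tells the reader that the CI is conditional on selection.

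It can also be said that the SAP never states outright that only retained factors get an odds ratio, and that the detailed programming specifications sit in a mock-output file not available here. That is fair. The 50% depends on the usual reading.

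Several stronger readings are tempting, and the documents or the arithmetic do not support them:
- A reader might infer that all the reported intervals lack their coverage. The failure is confined to null factors given retention; for true predictors, coverage was near or above nominal.
- A reader might infer that stepwise selection creates more false predictors. The overall rate is about 5% either way; selection changes which results are shown and how a shown result should be read.
- A reader might infer that leaving treatment unnamed causes the 50%. It does not. Nor does its absence from a list of baseline covariates prove that it is out of the model.
- A reader might infer that a false predictor would steer enrichment of a later trial. The documents describe no such use.
- A reader might infer that the protocol plans the same five-candidate model. Its candidate list is different.

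Finally, about five remissions per term is thin for a full model. That means wide intervals, but not a loss of coverage in the simulations.

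**Conclusion.** The point holds, as a minor one. If odds ratios are taken from the final selected model, the 95% CI for a factor with no true effect covers the truth about 50% of the time, given that the factor is retained. That figure follows from the plan's own 0.10 and 95% and barely moves across the simulated settings. Weak true effects are overstated when retained, about 1.57 for an assumed 1.30. Strong effects are not materially changed.

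The silence on treatment is a separate specification gap: the model is not fully defined until the SAP says how treatment enters.

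The exaggeration figures rest on an assumed rate for 30 mg, assumed covariate distributions and assumed effect sizes. The 50% does not depend on them. No primary or key secondary estimate or test is affected.

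**What to change.** Replace the stepwise paragraph in SAP 16.3. For each of the five endpoints, fit one prespecified logistic model with randomized treatment, the three stratification factors, ALC and CRP all forced in, and report every odds ratio with its 95% CI. ALC and CRP can go in on the log scale, as SAP 16.1.4.1 already does for imputation.

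If selection is kept, force treatment in, say which model the odds ratios come from, and label the CIs as post-selection and descriptive.

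Align Protocol 9.4.1.3 with the SAP. The protocol lists FCP and does not name the stratification factors; the SAP drops FCP and adds the factors. SAP Section 18, on departures from the protocol, should record the difference.

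The cost is one SAP paragraph and one line in Section 18, with no new data and less programming than stepwise selection. The downside is wide intervals for clinical remission, at about five events per term.
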